A wearable sleep device, WatchPAT, designed for home use has been utilized for the last 5 years clinically in adults. In July of 2016, the FDA approved the use of this device down to the age of 12 specifically for the oxygen saturation and apnea hypopnea index, but not the respiratory disturbance index (>17 years only). We have included the device company provided general description of the device, as well as the descriptions of limitation and use with individuals 12-17 years. As many of the limitations of pediatric use pertain to placement and utilization of the device, we will perform the sleep study while the patients are having their already planned and approved overnight stay in the hospital, and will have the device placed by our study personnel, who will be trained in correct placement and interpretation. Our study team also has extensive experience with similar devices from this company, and they are a supportive and easy to work with company.

Known obstructive sleep apnea or treatment with CPAP will not be an exclusion criteria, however, those individuals already utilizing CPAP at home will be requested to bring it for admission and use it during the WatchPAT study, so that we capture their typical home sleep patterns.

III. Research Methods

A. Outcome Measure(s):

Primary Outcome Measure(s): Activity ratios of the hepatic pentose phosphate pathway, TCA cycle and TG synthesis.

Secondary Outcome Measure(s): Peripheral IR as assessed with a 6.5 hour OGTT, measures of SNS activity, Hepatic fat content, hepatic phosphate profile. Targeted glucose and fat metabolism metabolomics, and untargeted exploratory analysis, gut microbiota profile.

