Power calculation: The primary outcome is hepatic substrate flux pathway percentages measured as PEP, TCA and TG synthesis pathways. Power analysis is based on publications utilizing similar methods, with the Primary Aim of understanding differences in hepatic metabolism in obese girls with PCOS who either have or do not have hepatic steatosis. The reference manuscript included 13 men without HS, and 6 men with HS⁵⁰. They found that during hyper-insulinemia, glycerol related gluconeogenesis was increased, as was the PEP cycle in individuals with HS compared to those without. Utilizing the PEP value, from this paper, the difference between the group means is 3 μ mol.min.kg FFM, and the standard deviation is 2 μ mol.min.kg FFM. Differences between the two primary groups (PCOS, controls) will be assessed with a t test or for non-normally distributed data a non-parametric test such as Mann-Whitney U. With 15 untreated PCOS with HS and 15 untreated PCOS without HS, we would have a power of 0.97 to detect an alpha of 0.05. Since the reference population is men who have more uniform hormone profiles, I am choosing to be overpowered should the variability in our population be greater. As the measurement is in kg of fat free mass, we will not have to do adjustments with BMI or weight. However, as African Americans are less likely to have HS, and Hispanics more likely to have HS, if ethnicity percentages are different between groups, we will need to adjust for ethnicity in our calculations.

Secondary Aims: a) For comparison of the PCOS to control groups, individuals will be matched in terms of HS status, so that the comparison is just between the hormonal state. I am assuming that there will be less of a difference between these groups, so with a difference of 2 Umol.min.kg FFM, and the standard deviation is 2, with 20 PCOS and 20 controls, we would have a power of 0.87 to detect a alpha of 0.05. b) For comparison of treatment with either metformin or OCP's, we will compare the untreated group to the treatments individually. We will not compare the two treatments to each other. I am assuming that there will be less of a difference between these groups, so with a difference of 2 Umol.min.kg FFM, and the standard deviation is 2, with 30 PCOS and 15 in a treatment group, we would have a power of 0.87 to detect a alpha of 0.05.

All measures will be adjusted for OSA status (yes/no) and/or severity of AHI.

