Overall Expected Results: We anticipate that we will determine which specific areas of hepatic metabolism are upregulated in girls with hepatic steatosis. This data would then provide the background evidence for future therapeutic trials. We will also refine this protocol and identify if metabolomics can be utilized to measure this type of hepatic energy flux.

Significance: Recent evidence in adults with PCOS indicates that 60-70% have NAFLD^{7,15}. Our data shows that > 45% of obese girls with PCOS have NAFLD, likely an underestimate due to exclusion criteria of T2D and weight >250 lbs in the previous protocols. The majority of NAFLD studies have focused on males, and none have been performed in multi-race cohorts of girls with PCOS, despite this high prevalence. NAFLD has been described as the primary driver of worsening metabolic syndrome and CVD in obesity across populations, and can progress to cirrhosis and liver failure^{5,6}. Thus, understanding the relative contributions of adipose and hepatic IR to NAFLD is critical to designing strategies to improve the long term health of these girls and reduce their risk of T2D, CVD and liver failure.

IX. References:

5. de Groot PC, Dekkers OM, Romijn JA, Dieben SW, Helmerhorst FM. PCOS, coronary heart disease, stroke and the influence of obesity: a systematic review and meta-analysis. *Human reproduction update* 2011;17:495-500.

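### Three pathways are jointly primary with no multiplicity rule, so the chance of at least one false pathway difference is about 10–14%, while power is stated for one pathway at 0.05

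*Combined protocol and SAP*

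**What the plan says.** Section III.A (Outcome Measures) gives the primary outcome as "Activity ratios of the hepatic pentose phosphate pathway, TCA cycle and TG synthesis". Section VII (Power calculation) names the same three: "The primary outcome is hepatic substrate flux pathway percentages measured as PEP, TCA and TG synthesis pathways". Section IV uses PEP as its abbreviation for the pentose phosphate pathway. Neither place ranks the pathways.

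The primary sample size argument compares untreated PCOS girls with and without HS, and rests on one pathway: "Utilizing the PEP value, from this paper", "the difference between the group means is 3" and "the standard deviation is 2" (both in µmol/min/kg FFM). With 15 girls per group the plan concludes "we would have a power of 0.97 to detect an alpha of 0.05". No effect size, SD or power is given for TCA or TG synthesis.

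Alpha appears only inside the power statements, and sidedness is not stated. Group differences "will be assessed with a t test or for non-normally distributed data a non-parametric test such as Mann-Whitney U". That sentence names PCOS and controls as the groups, although the power figure that follows is for HS versus no HS.

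Section VII contains no multiplicity adjustment, no testing order and no requirement that all three pathways succeed. Section VIII (Overall Expected Results) says: "We anticipate that we will determine which specific areas of hepatic metabolism are upregulated in girls with hepatic steatosis".

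**The concern.** With three equal primary outcomes and no rule linking them, the plan does not say what counts as a positive primary result. The aim in section VIII is to identify which pathways are raised, so a significant result on any one of them could be reported as the primary finding. The 0.05 in the power statement describes one test of one outcome. It does not describe the error rate of a set of three.

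What is at stake is the next step. The protocol says the results will support grant applications for treatment trials (section III.E) and future therapeutic trials (section VIII). A pathway that differs only by chance could become a treatment target.

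**Working it through.** **Inputs.** From section VII: three primary pathways; alpha 0.05; difference 3 and SD 2 for PEP; 15 versus 15. From section III.B and the enrolment table in III.C: 20 untreated PCOS girls. Correlations between pathways and the HS split among the 20 girls are not given, so they are assumptions here.

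**1. Reproduce the stated power and settle sidedness.** For a two-sample t test the noncentrality is δ / (SD·√(1/n₁ + 1/n₂)) = 3 / (2·√(1/15 + 1/15)) = 4.11, with 28 df.

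| Comparison | Stated | Two-sided 0.05 | One-sided 0.05 |
|---|---|---|---|
| 15 v 15, difference 3 | 0.97 | 0.977 | 0.991 |
| 20 v 20, difference 2 | 0.87 | 0.869 | 0.928 |
| 30 v 15, difference 2 | 0.87 | 0.871 | 0.929 |

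The plan's figures match a two-sided 0.05 test of a single outcome. They do not match a one-sided test.

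**2. Error rate over three tests.** Assume each pathway is tested at two-sided 0.05 and no pathway truly differs.

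- Any false difference, independent pathways: 1 − 0.95³ = 0.143. Upper bound under any dependence: 3 × 0.05 = 0.15.
- False upregulation only, independent pathways: each two-sided test puts 0.025 in that direction, so 1 − 0.975³ = 0.073. Upper bound: 3 × 0.025 = 0.075.

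Simulated t tests at 15 versus 15 (20,000 runs) with equally correlated pathways:

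| Assumed correlation | Any false difference | False upregulation |
|---|---|---|
| 0 | 14.2% | 7.4% |
| 0.3 | 13.6% | 6.7% |
| 0.5 | 12.9% | 6.6% |
| 0.8 | 10.3% | 5.1% |
| One test, for reference | 5% | 2.5% |

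Like for like, the inflation is about 2.9-fold near independence (14.3/5, or 7.3/2.5) and about 2-fold at correlation 0.8 (10.3/5, or 5.1/2.5).

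**3. PEP power if alpha is shared.** Holm's first step over three tests is 0.05/3 = 0.0167, two-sided.

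| Untreated girls, HS / no HS | Power at 0.05 | Power at 0.0167 |
|---|---|---|
| 15 / 15 (section VII) | 0.977 | 0.933 |
| 10 / 10 (20 planned, assumed split) | 0.887 | 0.755 |
| 9 / 11 (20 planned, assumed split) | 0.884 | 0.750 |

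The loss is 4 points in the first row and 13 in the other two. If the SD were 2.5 rather than 2 (an assumption), the 15/15 figures would be 0.887 and 0.765.

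**The case against.** The strongest reply is that this is a non-randomised, cross-sectional physiology study, using a tracer method the protocol itself describes as not yet validated in young people. No treatment or licensing decision rests directly on it. The opening hypothesis expects several hepatic pathways to move together, so reporting all three with intervals would be a defensible approach. This has some force: strict family-wise control is partly a matter of purpose. But the plan does not take that position. It applies the exploratory label to the untargeted analysis and the microbiota profile, and calls the three pathways primary.

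It is also fair to say that the plan nowhere states that each pathway is tested at 0.05, or that one positive test is enough. Both are inferences, from the absence of any adjustment and from the expected-results sentence in section VIII, which is not a decision rule. The inference is reasonable but should be presented as one.

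Two stronger readings are tempting and do not hold. A reader might infer a 14% chance of falsely declaring a pathway upregulated. The stated powers imply two-sided tests, so 14% is the risk of a false difference in either direction, and the upregulation figure is about 7% or less. A reader might also infer that the error rate is nearly three times nominal in all cases. That needs near-independence, and the documents give no correlation.

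**Conclusion.** The concern stands at this size. With three jointly primary pathways and no rule across them, the chance of at least one false HS versus no-HS difference is about 14% if the pathways are independent, at most 15%, and about 13% and 10% at correlations of 0.5 and 0.8. For a false upregulation it is about 5–7%. The single-test references are 5% and 2.5%. These figures assume that each pathway is tested at two-sided 0.05, that any one result may be reported, and that no pathway truly differs.

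The stated power of 0.97 is arithmetically sound for PEP tested alone with 15 girls per group. It says nothing about TCA or TG synthesis, and would not apply to PEP if alpha were shared.

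A reader might conclude from the 15/15 figures that an adjustment costs only about 4 points of power. The documents do not support that as a general statement: section VII needs 30 untreated PCOS girls, while sections III.B and III.C plan 20.

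**What to change.** **Preferred.** In sections III.A and VII, name PEP as the single primary outcome for the HS versus no-HS comparison, tested at two-sided 0.05, and list TCA and TG synthesis as secondary. This matches the only power calculation in the plan and costs no power. The price is that TCA and TG synthesis lose primary status, so a finding on either would be supportive only.

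**Alternative.** Keep all three as primary and apply Holm across them for the HS comparison. Restate PEP power at the first step: 0.93 if 15/15 untreated girls are really available, or about 0.75 (from 0.89) for 20 girls at an assumed 10/10 split. Add an assumed effect and SD for TCA and TG synthesis, since neither has one.

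Either route takes a sentence or two in the plan, which should also state that tests are two-sided. Before any power figure is printed, reconcile the number of untreated PCOS girls: 20 in sections III.B and III.C against 30 in section VII.

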Title: Post-Prandial Liver Glucose Metabolism in Polycystic Ovarian Syndrome (PCOS) and understanding Standard of Care Medications

Version Date: 8/17/2017

NCT03041129

COMIRB Protocol

COLORADO MULTIPLE INSTITUTIONAL REVIEW BOARD
[name] [contact] [contact]

Project Title: Post-Prandial Liver Glucose Metabolism in Polycystic Ovarian Syndrome (PCOS) and understanding Standard of Care Medications

Version Date: 8/17/2017

Principal Investigator: [name] [name], PhD

I. Hypotheses and Specific Aims:

HYPOTHESIS:

Obese girls with hepatic steatosis (HS) will have hepatic glucose metabolism that is upregulated towards de novo lipogenesis (DNL) via multiple intrahepatic pathways, compared to PCOS without HS and obese controls without HS. HS will be related to relative post-prandial hyperglycemia. Post-prandial hyperglycemia will be made worse or remain unchanged with oral contraceptives and better with metformin.

Specific Aims:

Aim 1: In obese girls with PCOS, post-prandial hepatic substrate metabolism will differ by HS status and treatment regimen and can be assessed with just an oral tracer protocol combined with NMR isotopomer analysis.

Hypothesis: Girls with HS will have upregulated post-prandial hepatic non-glycogenic metabolism compared to those without HS. This will be unchanged by oral contraceptives, and decreased with metformin.

Rationale: A marker of whole body DNL was increased in girls with HS, and preliminary work from my K23 project indicates that direct measures of DNL are elevated, but upstream alterations in intrahepatic metabolism are unclear. Oral contraceptives do not mitigate metabolic risk, whereas metformin decreases HS.

Methods: A 6.5 hour OGTT with an oral U-C₁₃glycerol tracer will be paired with NMR isotopomer analysis of serum samples to describe flux through the hepatic pentose phosphate pathway, TCA cycle and DNL pathways in girls with PCOS receiving lifestyle only, metformin or oral contraceptive treatment, and obese girls with regular menses receiving lifestyle therapy.

Aim 2: Describe the optimal timing for identifying metabolomics profiles associated with risk for T2D and HS.

Hypothesis: Metabolomics profiles between girls with HS and worse IR will differ the most between 3-6 hours.

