The protocol as described includes the entire subject set, which allow for comparisons between obese girls with and without PCOS. OGTT with an oral tracer will be conducted in all subjects. The specific points that are to be evaluated are listed below:

- 1) OGTT with glycerol tracers
 - a. Purpose: Develop an oral stimulus model to assess hepatic substrate flux
 - i. Question 1. Is 6.5 hours post oral load long enough to model hepatic and adipose insulin sensitivity?
 1. Rationale: In our current study (14-0542), we have found that 6 hours are required for metabolites to return to normal, we do not anticipate this to change greatly with the addition of the glycerol tracer.
 2. Measurement. Serum glucose and insulin will be measured post-glucose load for 6.5 hours in the first 6 subjects. If 6.5 hours post glucose values are within 20 mg/dL for glucose and 20 IU/mL for insulin relative to baseline values, 6.5 hours will be considered sufficient.
- 2) Measurement of Hepatic Substrate flux in youth.
 - a. Purpose: Optimize a model to asses hepatic substrate flux in youth looking at shifts from pentose phosphate pathway (PEP), TCA cycle and fatty acid synthesis
 - i. Rational: utilizing an oral glycerol model with NMR isotopomer analysis is a newer technique. It has not been validated in youth.
 - ii. Measurement: NMR isotopomer analysis with pathway flux calculations and modeling
 - iii. Revision plan if model not correct: 1) increase the amount of tracer given 2) increase the frequency of blood draws in the later sampling period.

Overall Project Limitations:

- 1) Subject recruitment is always a potential concern, but is minimized by a streamlined recruitment system and experience with this population; the previous, more intensive study is well tolerated in youth and enrolled faster than projected. In addition, we had >100 new PCOS referrals to our pediatric endocrinology department in 2013 alone, and the PI has a clinic specifically for girls with PCOS.
- 2) Subject drop-out: We expect reasonably good completion rates due to the non-invasive nature of the two study visits and our low dropout rate in our previous studies in control and PCOS adolescents using similar procedures.

V. Data Management and Security Plan

Data Entry

Data will be entered from paper forms. Once forms are completed, verified and corrected for inconsistencies, they will be manually entered at our site using a computerized data management system (Redcap).

Edit Checks

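### The primary outcome is named as percentages and as ratios without a denominator but powered as absolute flux; if it is a share of a total containing these pathways, it tests relative shift, not upregulation

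*Combined protocol and SAP*

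**What the plan says.** Three scales appear for one primary outcome.

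- **Percentages.** Section VII (Data Analysis Plan, Power calculation): "The primary outcome is hepatic substrate flux pathway percentages measured as PEP, TCA and TG synthesis pathways".
- **Ratios.** Section III.A (Outcome Measures): "Activity ratios of the hepatic pentose phosphate pathway, TCA cycle and TG synthesis". Numerator and denominator are not given.
- **Absolute flux.** The same power paragraph takes a PEP difference of 3 and an SD of 2, both in µmol per minute per kg FFM. It also argues that no BMI or weight adjustment is needed because the measurement is per kg FFM.

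No section says whether the three percentages add to 100, which scale enters the t test or Mann-Whitney test, or what the null hypothesis is.

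The claims are mostly worded as increases. The Aim 1 hypothesis (Section I) reads: "Girls with HS will have upregulated post-prandial hepatic non-glycogenic metabolism compared to those without HS". The Aim 1 methods promise to "describe flux through the hepatic pentose phosphate pathway, TCA cycle and DNL pathways". Section VIII expects that "we will determine which specific areas of hepatic metabolism are upregulated in girls with hepatic steatosis".

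Some wording is relative. The overall hypothesis speaks of "hepatic glucose metabolism that is upregulated towards de novo lipogenesis (DNL) via multiple intrahepatic pathways", and Section IV describes a model "looking at shifts from pentose phosphate pathway (PEP), TCA cycle and fatty acid synthesis".

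**The concern.** A group comparison of a pathway's share asks whether the mix of pathways differs. A comparison of its absolute rate asks whether the pathway runs faster. These are different nulls. When the denominator contains the pathways themselves, a proportional rise in all of them leaves every share where it was, and a rise in one lowers the shares of the others even though their rates have not moved.

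At stake is the study's main conclusion. Section VIII presents the answer to which areas are upregulated as background evidence for future therapeutic trials. On a share scale, a joint rise could be reported as no difference, and an unchanged or even rising pathway could be reported as reduced. The stated power would also belong to a different quantity from the declared outcome.

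**Working it through.** **1. The plan's own power figure.** Inputs from Section VII: difference 3, SD 2, 15 v 15, alpha 0.05 (two-sided assumed; the plan does not say). Noncentrality = 3 / (2 × √(1/15 + 1/15)) = 4.11 on 28 degrees of freedom, so the exact t-test power is 0.977. The stated 0.97 reproduces, but as power for absolute PEP flux. No mean or SD of a percentage is given, so power for the percentage outcome cannot be computed from the documents.

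**2. What happens to shares.** Share = pathway flux / total flux. The baseline of 8 per pathway is my assumption; the rise of 3 is the plan's.

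| Denominator | Scenario | Share before | Share after |
|---|---|---|---|
| Three pathways only | all rise by 3 | 8/24 = 33.3% each | 11/33 = 33.3% each |
| Three pathways only | PEP alone rises | 8/24 = 33.3% each | PEP 11/27 = 40.7%; others 8/27 = 29.6% |
| Three pathways + 24 unchanged units | all rise by 3 | 8/48 = 16.7% each | 11/57 = 19.3% each |
| Three pathways + 24 unchanged units | PEP alone rises | 8/48 = 16.7% each | PEP 11/51 = 21.6%; others 8/51 = 15.7% |

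Only a proportional rise leaves closed shares unmoved. With baselines 4/8/12 and a rise of 3 in each, the shares go from 16.7/33.3/50.0% to 7/33, 11/33 and 15/33, that is 21.2/33.3/45.5%. The largest pathway's share falls although its flux rose.

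**3. How often the tests reject.** Simulation with 10,000 trials per scenario, a two-sample t test at two-sided 0.05 for each pathway, 15 v 15, normal flux with SD 2. Assumptions not in the documents: the baselines, a between-pathway correlation of 0 to 0.5, and the denominators.

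| Setting | Result |
|---|---|
| Absolute flux, all rise by 3 | about 98% per pathway |
| Closed shares, equal baselines 6–12, all rise by 3 | about 5% per pathway |
| Closed shares, equal baselines 6–12, PEP alone rises | each unchanged pathway flagged about 31–58% |
| Closed shares, baselines 4/8/12, all rise by 3 | smallest and largest pathways flagged about 50–71% each, the largest in the wrong direction |
| Open total (+24 unchanged units), baseline 8, all rise by 3 | about 53–73% per pathway |
| Open total (+24 unchanged units), baseline 8, PEP alone rises | each unchanged pathway flagged about 11–14% |

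Lognormal flux with baselines 6 to 10 gives the same picture: 90–94% on absolute flux against 4.7–5.4% on shares for a joint proportional rise, and 30–58% flags for unchanged pathways.

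**4. External reference.** If each ratio is taken to a quantity outside these pathways that does not differ between groups, 8/k becomes 11/k for a pathway that rises and stays 8/k for one that does not. Neither effect occurs.

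**The case against.** The strongest reply is that the documents never commit to shares of a closed total. No denominator is given, and the power and BMI/weight statements in Section VII read like an absolute-rate analysis. This stands. A reader might infer that the planned test's null is equal shares, so that the trial will miss a general rise and flag unchanged pathways. The documents do not establish that: it needs a t test on percentages that sum to 100 over three pathways, which no section states.

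Second, the hypothesis is partly relative. The phrase "upregulated towards de novo lipogenesis (DNL) via multiple intrahepatic pathways", the shift towards lipogenesis described in Section II.b and the shifts in Section IV all suit a share or ratio. The text also does not say that every pathway rises, or rises proportionally, and the non-glycogenic wording of Aim 1 may point to a denominator that includes glycogenic flux. This stands too, but Aim 1's own hypothesis and Section VIII are not worded as shifts.

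Third, the 5% figure needs equal baselines and a closed total. With unequal baselines a joint rise does move shares, and other flux in the denominator weakens both effects. That is correct. Uneven rises do not rescue the interpretation, though, because a rising pathway can then show a falling share.

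**Conclusion.** The point holds as a conditional one. It is certain from the text that the primary outcome has two names, no denominator, and a power calculation on a third scale, while the aims and expected results promise statements about upregulation. With any denominator that contains these pathways, a difference in a percentage cannot by itself show that a single pathway is upregulated.

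The size depends on the undefined denominator. The worst case examined is about 5% against 98% detection of a joint rise, with 31–58% flags for unchanged pathways. An intermediate case, with 24 further unchanged units, is 53–73% detection and 11–14% flags. With an external unchanging reference there is no problem. All of these rest on assumed baselines and correlations. They do not support saying that the trial as planned will miss a general rise. The 0.97 stands for absolute PEP flux under the plan's inputs and should not be read as power for percentages.

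**What to change.** State one scale and one denominator for the primary outcome, in the same words in Sections III.A and VII, and say which quantity enters the test.

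Base any claim that a single pathway is upregulated on its absolute rate per kg FFM. That is the scale on which the 0.97 (for PEP) already holds and to which the BMI/weight argument applies. Report percentages or ratios only as evidence of a relative shift, as log-ratios if they share a total. Log-ratios between these pathways stop a rise in one from being counted as a fall in all the others. They do not detect a proportional joint rise (about 5% rejection with equal baselines), so they cannot replace the absolute rate.

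The documents do not settle whether the oral tracer yields an absolute rate. If it does not, reword the hypotheses in Section I and the expected results in Section VIII to a relative shift towards a pathway, and do not quote 0.97 as the power for the percentage outcome.

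The cost is wording in four sections and a transformation of data already to be produced; no new data collection. The downside is that the claim may become narrower.

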Likely contributors to above measures: Lipid/glucose markers:(fasting C-peptide and lipid panel, HbA1c); hepatic markers:(c-reactive protein, glucagon, GLP-1 and leptin at baseline, 5 min and 30 min post glucose load to asses change with OG, adiponectin, AST, ALT, GGT), sex-steroids:(DHEAS, free and total testosterone, sex hormone binding globulin, progesterone, estradiol); Body size and composition: (BMI, waist/hip ratio, DEXA, hepatic visceral fat via MRI³⁶⁻³⁹), Whole body fat oxidation at rest and following glucose ingestion as measured with a metabolic cart; Physical activity/ diet:(accelerometer, activity survey (3DPAR); Food frequency survey).Questionnaires for presence of obstructive sleep apnea. Questionnaires for perceived mental strengths and difficulty (note there is no assessment of suicidality on this tool). Obstructive Sleep Apnea, to be assessed with an overnight sleep study via WatchPAT.

B. Description of Population to be Enrolled:

Study staff aims to enroll 20 obese girls with regular menstrual cycles, 20 girls with un-treated PCOS, 20 girls with PCOS treated with at least 6 months of Metformin and 20 girls with PCOS treated with at least 6 months of oral contraceptives. The PCOS groups will be compared to 20 obese non-PCOS controls. This is the number of participants needed to be completed statistically, thus more subjects may be enrolled, to allow for screen failures and dropouts. Total enrollment will be up to 100 participants.

Ethnic Categories	Gender		
	Females	Males	Total
Hispanic or Latino	40	0	40
Not Hispanic or Latino	60	0	60
Ethnic Categories: Total of All Subjects	100	0	100
Racial Categories			
American Indian/Alaska Native	5	0	5
Asian	10	0	10

Native Hawaiian or Other Pacific Islander	10	0	10
Black or African American	32	0	32
White	43	0	43
Racial Categories: Total of All Subjects*	100	0	100

Inclusion Criteria:

- 1) Female
- 2) Ages 12-21
- 3) Sedentary- less than 2.5 hours of moderate (jogging, swimming etc) exercise a week.
- 4) BMI equal or greater than the 90th percentile for age and gender
- 5) For PCOS groups: (NIH definition) irregular menstrual cycles at least 1.5 years after menarche and either clinical evidence of hyperandrogenism or elevated Testosterone (above the norms for age/tanner stage) at time of screening or documented prior to initiation of therapy for OCP and metformin groups.

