DEXA Scan (located in Leprino building)			X
Oral Glycerol Tracer			X
WatchPAT sleep study			X
EndoPat and Dynapulse		X	
MRI of abdomen and liver,		X	
P MRS of Liver (pending scheduling)		X	
Metabolic Cart			X
Total Time of visit (approximately)	2 Hours	2 Hours	24 Hours
Location of Visit	CHCO CTRC Outpatient	UCD Outpatient Brain Imaging Center	CHCO Inpatient Hospital

The study consists of 3 visits - 2 outpatient visits and one overnight inpatient visit. Inpatient visit will last approximately 24 hours, outpatient screening visit approximately 2 hours, outpatient MRI visit approximately 2 hours. The 3 visits would be completed within 4 months' time.

Overall enrollment procedure plan per group

Test Group	Screening	MRI/MRS	Overnight stay	Oral Glycerol tracer	DEXA
Untreated PCOS	25	20	20	20	20
PCOS w/ Metformin	25	20	20	20	20
PCOS w/ OCP's	25	20	20	20	20
Obese Control	25	20	20	20	20
Total	100	80	80	80	80

VISIT 1 (SCREEN VISIT)

Pediatric CTRC Outpatient unit: Participants will begin with a medical screening and physical exam for inclusion/exclusion criteria evaluation. During this visit, patients will review and complete consent documents, have demographics and medical history confirmed, assess allergies and further evaluation of inclusion/exclusion criteria, have blood samples drawn, and have anthropometrics completed. HbA1c, ALT, AST, CBC panel and testosterone panel will be drawn at the beginning of the visit after consent in all subjects. PCOS subjects will have more labs performed for confirmation of PCOS status, if not performed previously.

Screening lab test	Purpose for test
HbA1C	Rule out type 2 diabetes, if > 6.4% subject to be excluded
ALT, AST	Ensure no severe liver disease, if >150 IU subject to be excluded normal subject is excluded
Hemoglobin & Hematocrit (part of CBC)	If subject is Anemic, they will be excluded
Testosterone	Test for hyperandrogenism – required to meet NIH criteria for PCOS
Optional PCOS labs	
PCOS status must be confirmed prior to enrollment in PCOS group. Referring physicians often do not perform the entire recommend work-up for oligomenorrhea (per 2013 Endocrine Society Clinical Guidelines for PCOS). The values are typically expected in PCOS publications	
TSH, total T4	Ensure no hypo or hyperthyroidism causing amenorrhea
LH, FSH	Rule out primary ovarian failure
17-hydroxyprogesterone	Rule out late onset congenital adrenal hyperplasia
DHEAS	Rule out adrenal tumor
Prolactin	Rule out prolactin secreting brain tumor

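### The primary power of 0.97 assumes 30 untreated PCOS girls, but the enrolment plan provides 20 and sets no quota by hepatic steatosis (HS)

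*Combined protocol and SAP*

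**What the plan says.** The primary comparison is between untreated girls with PCOS who have HS and those who do not. The Power calculation in section VII takes a difference of 3 and an SD of 2 from a study of 19 men (13 without HS, 6 with), sets alpha at 0.05, and states: "With 15 untreated PCOS with HS and 15 untreated PCOS without HS, we would have a power of 0.97". It justifies the size because the reference data come from men: "I am choosing to be overpowered should the variability in our population be greater". Secondary aim b) in the same section again uses 30 untreated girls, "with 30 PCOS and 15 in a treatment group".

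Section III.B plans four groups of 20, among them "20 girls with un-treated PCOS", and says: "This is the number of participants needed to be completed statistically". More may be enrolled only to cover screen failures and dropouts, and "Total enrollment will be up to 100 participants". In section III.C, the table headed "Overall enrollment procedure plan per group" gives every group 25 screened and 20 studied, 80 studied in all.

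The eligibility criteria do not mention HS. Liver fat is measured by MRI at Visit 2, after screening. On how common HS is, section VIII gives above 45% for the investigators' own girls with PCOS and calls that a likely underestimate. For adult women with PCOS, section II.b gives 50–70% and section VIII 60–70%.

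**The concern.** The section that justifies the sample size needs 30 untreated girls, while the section that calls its numbers the statistical requirement provides 20. Even if all 25 girls screened for that group were studied, there would not be 30. A reader cannot tell which size the primary comparison will have.

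The 0.97 is the only power figure for the primary aim. It also carries the claim that the study can absorb more variability in adolescent girls than was seen in the reference men. If 20 is the true number, the power is lower and most of that reserve goes. The 15/15 split is a second open point: nothing in the enrolment plan produces it, and an uneven split lowers power further.

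**Working it through.** **Inputs.** From section VII: difference 3, SD 2, alpha 0.05, t test. Sidedness is not stated. I assume two-sided, because it gives 0.977 at 15/15, close to the stated 0.97; one-sided gives 0.991. Group sizes come from sections VII, III.B and III.C, and HS rates from sections II.b and VIII.

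**Formula.** Power = P(|T| > c), where T is noncentral t with n1 + n2 − 2 degrees of freedom, noncentrality (3/SD)/√(1/n1 + 1/n2), and c is the 0.975 quantile of central t.

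**The plan's own figure.** For 15/15 at SD 2 the noncentrality is 1.5/√(2/15) = 4.108, with 28 df and c = 2.048. Power is 0.977, so the stated value reproduces.

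**Twenty untreated girls.** For 10/10 the noncentrality is 1.5/√(2/10) = 3.354, with 18 df and c = 2.101. Power is 0.887. Other splits follow in the same way.

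| Split | Power, SD 2 | Power, SD 2.5 | Power, SD 3 | Largest SD with 80% power |
|---|---|---|---|---|
| 15/15 | 0.977 | 0.887 | 0.753 | 2.83 (42% above 2) |
| 10/10 | 0.887 | 0.718 | 0.562 | 2.26 (13%) |
| 9/11 | 0.884 | 0.714 | 0.558 | 2.25 (13%) |
| 14/6 | 0.828 | 0.643 | 0.492 | 2.08 (4%) |

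Splits of 12/8 and 13/7 give 0.874 and 0.857 at SD 2. The plan gives no SD for girls, so SD 2.5 and 3 are assumptions for illustration.

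**All 25 screened girls studied.** The best split, 12/13, gives 0.948, still short of 0.97.

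**HS split left to chance.** Average power = Σ P(k girls with HS) × power(k, n − k), with k binomial(n, HS rate), at SD 2:

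| HS rate | n = 20 | n = 30 |
|---|---|---|
| 45% | 0.865 | 0.971 |
| 50% | 0.869 | 0.973 |
| 60% | 0.852 | 0.966 |
| 70% | 0.793 | 0.936 |

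The 60% and 70% rows use adult rates. The document gives no upper value for girls.

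**Secondary aim b)** (difference 2, SD 2). The noncentrality is 1/√(1/30 + 1/15) = 3.162 for 30/15 and 1/√(2/20) = 3.162 for 20/20. Power is 0.871 and 0.869, so the conflict in group sizes does not matter numerically here.

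**Possible source.** 30 untreated + 15 metformin + 15 oral contraceptive + 20 controls = 80, the same total as 4 × 20. Section VII may reflect a different allocation of the same 80 girls, but no section states that allocation.

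**Not included.** All figures precede the adjustment in section VII, "All measures will be adjusted for OSA status (yes/no) and/or severity of AHI", and the conditional adjustment for ethnicity.

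**The case against.** The arithmetic behind 0.97 is right, and the document does not show which section is in error. Section VII uses 30 untreated girls twice, and 30/15/15/20 gives the same 80 completers. If that was intended, 0.97 stands and only the counts in sections III.B and III.C are wrong. This holds: the loss of power is conditional on 20 being the true number. The contradiction remains in either case.

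At the plan's own difference and SD, 20 girls still give more than 0.80 for fixed splits from 10/10 to 14/6, and for chance splits up to about 69% HS. The 0.79 arises only at the top of the adult range, and the larger shortfalls need an SD that the plan does not state. This also holds, and the figures should carry those labels. But greater variability than in the reference men is the risk the plan itself names, so its effect at 20 girls belongs in the assessment.

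Finally, the split need not be left to chance. Section VII matches on HS status for the PCOS–control comparison, and section II reports liver fat from an earlier protocol whose participants may be re-contacted, so selecting girls by known HS status is conceivable. No section says it will be done for the primary comparison, so the 15/15 split remains an assumption.

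**Conclusion.** The concern holds. The stated primary power rests on 30 untreated girls, and the enrolment plan provides 20 with no arrangement for the HS split. If 20 is correct, power is at most 0.887 rather than 0.97. It is 0.83 to 0.89 for fixed splits from 14/6 to 10/10, and it falls to 0.79 on average for a chance split at 70% HS. The margin for a larger SD shrinks from 42% to 13% or less, so the statement about being overpowered is no longer well supported. If 30 is correct, the counts in sections III.B and III.C are wrong.

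These results assume a two-sided t test, the plan's difference of 3 and SD of 2 unless another SD is shown, and no covariate adjustment. Because the conflict concerns the size of the primary comparison, it must be corrected.

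**What to change.** First decide which allocation is intended, then make sections III.B, III.C and VII agree.

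**If 20 untreated girls is kept:**
- Replace the 0.97 sentence with power for 20 at the expected HS split: 0.88 at 9/11 and 0.83 at 14/6. Add the chance-split averages of 0.86–0.87 at 45–50% HS and 0.79 at 70%, the last marked as an adult rate.
- Replace the overpowering sentence with power under larger SDs, marked as assumed. For splits from 14/6 to 10/10 this is 0.64–0.72 at SD 2.5 and 0.49–0.56 at SD 3.
- State that the figures precede adjustment for OSA and ethnicity.
- Restate secondary aim b) as 20 versus 20, power 0.87.

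This costs only wording, though the stated power becomes less favourable.

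**If 30/15/15/20 was intended:**
- Correct the group sizes in sections III.B and III.C and the untreated screening number of 25.
- Say how 15 girls with HS and 15 without will be obtained. If the split is left to chance, give the power for 30 girls as 0.97 at 45–50% HS and 0.94 at 70%.

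The total stays at 80 completers. At the table's 25:20 ratio, screening is 37.5 + 18.75 + 18.75 + 25 = 100. Rounded up by group it is 38 + 19 + 19 + 25 = 101, one above the stated maximum, so the cap or one group's screening number needs a small adjustment.
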